6.5 Safety

6.5.1 Physical examination

An overall physical examination will be performed by the investigational staff at visit 2 and include the examination of general appearance, skin, neck (including thyroid), eyes, ears, nose, throat, lungs, heart, abdomen, back, lymph nodes, extremities, vascular and neurological. A short physical exam will include the examination of general appearance and vital signs (blood pressure and pulse) and will be performed at all visits starting from visit 3.

Detailed information on each evaluated apparatus from all physical examinations must be included in the source documentation at the study site.

Metabolic syndrome will require any 3 of the following 5 criteria: increased waist circumference (≥ 102 cm for men, ≥ 88 cm for women), elevated triglycerides (≥ 150 mg/dl), reduced high-density lipoprotein (HDL) cholesterol (≤ 40 mg/dl in men and ≤ 50 mg/dl in women), elevated blood pressure (≥ 130 mmHg systolic and ≥ 85 mmHg diastolic or ongoing treatment for hypertension) or elevated glucose (≥ 100 mg/dl or ongoing treatment for elevated glucose) ([Expert Panel JAMA 2001](#)).

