Normal blood pressure will be defined as a systolic pressure of 90 to <120 mmHg, and a diastolic blood pressure of 60 to <80 mmHg. Notable blood pressure will be hypertension (systolic blood pressure of ≥ 140 mmHg and/or diastolic blood pressure of ≥ 90 mmHg) or hypotension (systolic blood pressure of <90 mmHg and/or a diastolic blood pressure of <60 mmHg). A blood pressure indicative of prehypertension (systolic blood pressure of 120 to

<140 mmHg and/or diastolic blood pressure of 80 to <90 mmHg) will not be regarded as notable.

A normal pulse rate will be defined as a rate of 60 to 100 beats per minute (bpm). Notable pulse rates are a rate below 60 bpm (bradycardia) or above 100 bpm (tachycardia). Whether action needs to be taken to address notable vital signs will be decided by the investigator, taking into account the overall status of the patient. No specific action is foreseen as part of the study protocol.

14 Appendix 2: Liver event definitions and follow-up requirements

Table 14-1: Liver Event Definitions

	Definition/ threshold
Adverse event of special interest	
Laboratory values	ALT or AST > 3 x ULN ALP > 2 x ULN TBL > 1.5 x ULN
Medically significant event (SAE)	
Laboratory values	ALT or AST > 5 x ULN (with or without TBL > 2 x ULN [mainly conjugated fraction]) ALP > 5 x ULN (with or without TBL > 2 x ULN [mainly conjugated fraction]) TBL > 3 x ULN Potential Hy's Law cases (defined as ALT/AST > 3 x ULN and TBL > 2 x ULN [mainly conjugated fraction] without notable increase in ALP to > 2 x ULN)
Adverse events	Any clinical event of jaundice (or equivalent term) ALT or AST > 3 x ULN accompanied by general malaise, fatigue, abdominal pain, nausea, or vomiting, or rash with eosinophilia Any event that links to a preferred term (PT) in the MedDRA dictionary falling under the SMQ sub-module "Drug-related hepatic disorders – severe events only"* or any "Hy's law case" PT

* These events cover the following: hepatic failure, fibrosis and cirrhosis, and other liver damage-related conditions; non-infectious hepatitis; benign, malignant and unspecified liver neoplasms

Table 14-2: Liver Event Follow Up Requirements

Criteria	Event type	Actions required	Follow-up monitoring
Potential Hy's Law case ^a	Medically significant	Discontinue the study drug immediately Hospitalize, if clinically appropriate Report to Novartis as an SAE Establish causality	ALT, AST, TBL, Alb, PT, ALP and γ GT until resolution ^c (frequency at investigator discretion)

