2.3.2 Patient demographic and other baseline characteristics

Summary statistics n, mean, median, standard deviation, minimum, maximum, first and third quartiles will be presented for continuous variables for each cohort and overall on the Safety set. The number and percentage of patients in each category will be presented for categorical variables for each cohort and overall on the Safety set.

The following demographic and baseline variables will be summarized:

Demographic variables:

Continuous variables:

- Age (years)
- Height (cm)
- Weight (kg)
- Waist (cm)
- BMI (kg/m^2) will be calculate as (body weight in kilograms) / (height in meters)²

Categorical variables:

- Age categories (<65, >=65)
- Sex (Male, Female)
- BMI categories (<25 vs >=25)
- Race (Caucasian, Black, Asian, Native American, Pacific Islander, Unknown, Other)
- Ethnicity (Hispanic or Latino, Chinese, Japanese, Indian, Mixed Ethnicity, Other)
- Geographical region (north vs south/central)
- Smoking status at baseline
 - Never
 - Current
 - Former

Baseline disease characteristics variables:

Continuous variables:

- Baseline PASI score
- Baseline IGA mod 2011 score
- Age at diagnosis of psoriasis (years)
- Time since first diagnosis of psoriasis (years) (which is derived as date of baseline visit-date of first diagnosis of psoriasis)
- Time since first diagnosis of psoriatic arthritis (years) (which is derived as date of baseline visit-date of first diagnosis of psoriatic arthritis)

Categorical variables:

- Type of psoriasis history at diagnosis
 - Plaque type psoriasis
 - Nail psoriasis
 - Scalp psoriasis
- Number of patients with psoriatic arthritis
 - Type of psoriatic arthritis
 - Polyarticular
 - Monoarticular
 - Axial
 - Enthesitis
 - Dactylitis
- Quantiferon TB-Gold test
 - Negative
 - Positive
 - Indeterminate
- PPD test
 - Negative

- Positive
- Indeterminate
- TNFα 308 polymorphism
 - Heterozygous
 - Homozygous
- Metabolic syndrome
 - Yes
 - No

Definition of metabolic syndrome

Metabolic syndrome is defined as the presence of at least 3 of the 5 following criteria(Expert Panel JAMA 2001) :

- Increased waist circumference (≥ 102 cm for men, ≥ 88 cm for women).
- elevated triglycerides ($\geq 150 \text{ mg/dl}$).
- Reduced high-density lipoprotein (HDL) cholesterol ($\leq 40 \text{ mg/dl}$ in men and $\leq 50 \text{ mg/dl}$ in women).
- Elevated blood pressure (≥ 130 mmHg systolic and ≥ 85 mmHg diastolic or ongoing treatment for hypertension).

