- Elevated glucose (≥100 mg/dl or ongoing treatment for elevated glucose)

In order to interpret results adequately, the homogeneity of patient distribution between cohorts will be tested on selected baseline demographics and anamnestic variables (e.g. for gender, age, race, ethnicity, BMI, baseline PASI, baseline IGA, $TNF\alpha$ - 308 polymorphism, metabolic syndrome, smoking).

Categorical variables – as race, ethnicity, geographical region and type of PsA will be analyzed by Cochran-Mantel-Haenszel, while the remaining variables listed in the table below will be analyzed by means of a regression logistic model.

Continuous variables will be analyzed by means of an ANCOVA model corrected as indicated in the table below.

Number of patients with presence of PsA will be analyzed by means of Chi Square test.

Moreover, differences between cohorts in BMI, height, weight, waist, geographical distribution, type of psoriasis, age at PsO diagnosis, time since PsO diagnosis, concomitant PsA, type of PsA, time since PsA diagnosis, quantiferon TB-Gold, PPD test will be also explored. Variables reported in the table below will be included as covariates in the explanatory analysis model.

Normality data distribution will be assessed by means of Shapiro-Wilk test and with graphical methods (if possible). In case of non-normality, a non-parametric test will be used, if feasible.

Variable analyzed	Covariates/stratification factors
Age/ age group	Sex

Sex	Age
BMI/height/weight/waist/ BMI categories	Age, sex
Type of PsO (other than plaque)/ Time since PsO diagnosis/ age at PsO diagnosis/ presence of PsA/ time since PsA diagnosis/ metabolic syndrome	Age, sex, waist
PASI at baseline / IGA at baseline	Age, sex, waist, type of PsO, time since PsO diagnosis, presence of PsA
Race/ethnicity/geographical region/ Type of PsA	none
Smoking status	Age, sex
TNF-alpha polimorphism / quantiferon / PPD	Age

Medical history

Any condition entered as medical history or current medical conditions at baseline will be coded using the MedDRA dictionary version 18.1 or latest available. They will be summarized by system organ class (SOC) and preferred term (PT) of the MedDRA dictionary on the Safety set and will be presented by cohorts and overall.

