2.5.2 Statistical hypothesis, model, and method of analysis

The proportion of patients who reach PASI 90 at 16 weeks will be presented with the one-tailed 97.5% confidence interval of the Cw6 positive (POS) – Cw6 negative (NEG) difference.

The null hypothesis:

H0: Cw6 POS - Cw6 NEG \ge 0.12: The difference in proportion of patients achieving PASI 90 response between the Cw6-positive cohort (Cw6 POS) and the Cw6-negative cohort (Cw6 NEG) is at least 12%.

The alternative hypothesis:

HA: Cw6 POS - Cw6 NEG < 0.12: The difference in the proportion of patients achieving PASI 90 response between the Cw6-positive cohort (Cw6 POS) and the Cw6-negative cohort (Cw6 NEG) is less than 12%.

The proportion of PASI 90 response by cohort as well as the difference between cohort together with 97.5% upper CI will be provided using Clopper Pearson CI method.

A logistic regression analysis model will also be fitted, considering age, geographical region (i.e. north vs south vs central), BMI categories (<25 vs >=25), waist circumference, smoking status (Yes vs No), metabolic syndrome (yes vs no), previous PsO therapy (naïve vs previous systemic therapy vs previous biologic therapy), PsA (yes vs no), age at diagnosis of psoriasis, TNF α -308 polymorphism, IGA mod 2011 (severe, moderate, mild) as strata factors.

Model selection:

If model does not converge due to particular covariate(/s), the corresponding covariate(/s) will be removed from the model using Stepwise selection method until model get converged.

Interpretation:

We can conclude that PASI 90 response in the Cw6-negative cohort is not less than 12% with respect to the Cw6-positive cohort if the upper bound of the 97.5 % CI of the difference (Cw6 POS - Cw6 NEG) is less than the non-inferiority margin of 12%.

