2.8.4.3 Vital signs

Vital signs data (sitting pulse rate, sitting systolic and diastolic blood pressure) will be summarized on Safety set.

Summary statistics of vital signs and changes from baseline will be provided by visit and cohort. Clinically notable vital signs (Table 2.8.4.3) will be listed and absolute and relative frequencies will be presented by visit and cohort.

Vital sign (unit) parameter	Notable abnormalities
Systolic blood pressure (mmHg)	>= 140 mmHg or < 90 mmHg
Diastolic blood pressure (mmHg)	>=90 mmHg or <60 mmHg
Pulse (bpm)	> 100 bpm or <60 bpm

 Table 2.8.4.3
 Criteria for notable vital sign abnormalities

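### For untreated patients the metabolic-syndrome rule needs both pressures raised, so it rejects readings that the protocol itself calls hypertension and can only under-count the syndrome

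*SAP*

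**What the plan says.** SAP 2.3.2 sets the count rule: "Metabolic syndrome is defined as the presence of at least 3 of the 5 following criteria". The blood-pressure item in that list is "Elevated blood pressure (≥ 130 mmHg systolic and ≥ 85 mmHg diastolic or ongoing treatment for hypertension". Protocol 6.5.1 has the same condition: "elevated blood pressure (≥ 130 mmHg systolic and ≥ 85 mmHg diastolic or ongoing treatment for hypertension". No other section says that one raised pressure is enough.

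Two other places classify blood pressure. Protocol Appendix 1 (Blood Pressure and Heart Rate) defines hypertension as "systolic blood pressure of ≥ 140 mmHg and/or diastolic blood pressure of ≥ 90 mmHg". SAP Table 2.8.4.3 gives systolic and diastolic pressure separate rows; the systolic row reads ">= 140 mmHg or < 90 mmHg".

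The derived yes/no variable is then used as follows:
- **Baseline comparison (SAP 2.3.2).** The SAP says that "the homogeneity of patient distribution between cohorts will be tested on selected baseline demographics and anamnestic variables", and metabolic syndrome is among the examples it lists.
- **Adjusted PASI 90 logistic model (SAP 2.5.2).** It enters as "metabolic syndrome (yes vs no".
- **Secondary efficacy models (SAP 2.7.2).** It enters the propensity score, the MMRM fitted without the propensity score, the PASI 75 model and the IGA 0/1 model.

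**The concern.** The syndrome cut-off (130/85) is lower than the Appendix 1 hypertension cut-off (140/90), so every reading that meets the higher one should meet the lower one. As written, it does not. An untreated patient can be hypertensive in the vital-signs tables and have normal blood pressure in the baseline table of the same report.

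The cohorts are defined by genotype and are not randomised, so baseline comparisons and covariate adjustment are how the plan deals with imbalance. The Amendment 1 rationale records that the regulator named metabolic syndrome among the factors that the original protocol had left out. If the variable is misclassified, its prevalence by cohort is under-reported and the adjustment uses a poorer version of the factor that was asked for.

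**Working it through.** **Figure to reproduce.** The documents give no prevalence for the syndrome or for elevated blood pressure. The check is therefore one of logic, followed by an illustration of size.

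**Rules compared** (S = systolic, D = diastolic, T = on antihypertensive treatment):
- Written rule (SAP 2.3.2, protocol 6.5.1): (S ≥ 130 and D ≥ 85) or T.
- Either-pressure rule: S ≥ 130 or D ≥ 85 or T.
- Appendix 1 hypertension: S ≥ 140 or D ≥ 90.

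Bracketing the written rule the other way, S ≥ 130 and (D ≥ 85 or T), gives the same result for untreated patients.

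| Reading | Treated | Written rule | Either-pressure rule | Appendix 1 |
|---|---|---|---|---|
| 150/80 | no | not elevated | elevated | hypertension |
| 128/92 | no | not elevated | elevated | hypertension |
| 138/80 | no | not elevated | elevated | not hypertension |
| 145/92 | no | elevated | elevated | hypertension |
| 150/80 | yes | elevated | elevated | hypertension |

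**Direction.** Over all whole-number readings with S from 80 to 220 and D from 40 to 130, untreated, no reading is elevated under the written rule but not under the either-pressure rule. No Appendix 1 hypertensive reading is missed by the either-pressure rule. Any difference between the two rules is therefore an under-count by the written one.

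**Effect on the 3-of-5 count.** Take an untreated 150/80 patient who meets k of the other four criteria:
- k = 0 or 1: No under both rules.
- k = 2: No under the written rule (2 of 5), Yes under the either-pressure rule (3 of 5).
- k = 3 or 4: Yes under both rules.

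Only k = 2 changes status.

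**Illustrative size.** The share of patients changing from No to Yes is d × (1 − t) × q, where
- d = probability that exactly one pressure is raised in an untreated patient = P(either raised) − P(both raised);
- t = proportion on treatment;
- q = proportion with exactly two of the other four criteria.

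All inputs are assumptions: bivariate normal pressures with means 125/78 to 135/83, SD 15/10 and correlation 0.5 to 0.7; t from 15% to 30%; q from 20% to 35%; the three factors independent of each other. Half-unit cut-points (129.5 and 84.5) allow for whole-number recording.

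| | P(both) | P(either) | d | 1 − t | q | Share | Of 406 |
|---|---|---|---|---|---|---|---|
| Low end (125/78, correlation 0.7) | 0.197 | 0.443 | 0.245 | 0.70 | 0.20 | 0.034 | 14 |
| High end (135/83, correlation 0.5) | 0.358 | 0.725 | 0.367 | 0.85 | 0.35 | 0.109 | 44 |

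**Primary test.** Under SAP 2.5.2 the conclusion depends on the upper confidence bound of the Cw6 POS − Cw6 NEG difference against 12%; the logistic model is fitted in addition. The sample size does not use the syndrome either. With 80% response in both cohorts and 219 and 146 patients, SE = √(0.16/219 + 0.16/146) = 0.0427, 0.12/0.0427 − 1.96 = 0.85, and power is 80.2%. That agrees with the plan's 80% and has no syndrome input.

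**The case against.** **Appendix 1 and Table 2.8.4.3 serve another purpose.** They define notable vital signs for safety reporting and do not set the syndrome rule. That is correct. They still show that the plan is inconsistent, because a difference in purpose does not explain why a lower threshold should exclude readings that meet a higher one.

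**The *and* may only be listing two cut-offs.** The neighbouring HDL item uses *and* to join the limits for men and women. This is a fair point about intent, and the documents do not show how the variable was programmed. But the HDL limits apply to different people, whereas the two pressures belong to one patient. A programmer following the text would require both. If the meaning is in doubt, the derivation still needs to be stated.

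**The effect on the adjusted results may be small.** The logistic model, the propensity score and the MMRM without it already contain age, BMI category and waist circumference. Nothing in the documents suggests that a single raised pressure differs by Cw6 status. This stands: a reader might infer that the adjusted cohort comparison is materially biased, but no estimate supports that.

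**Not every odd-looking reading is a contradiction.** A reader might count 132/86, which is elevated here but not hypertension in Appendix 1. It is elevated under either wording and simply lies between the two thresholds.

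**HDL may be missing.** The chemistry panels listed in the protocol and SAP name cholesterol but not HDL. That is a separate matter, but if HDL is not captured, the proportion with exactly two other criteria in this trial may differ from the range assumed above.

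**Conclusion.** The criterion is wrong as written in both documents. It rejects untreated patients whom the protocol calls hypertensive, and against an either-pressure rule the error goes in one direction only. This conclusion rests on the text alone and needs no assumption about blood pressure in the trial population.

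The size does rest on assumptions. About 3% to 11% of patients would change from No to Yes under the ranges shown. Treated patients are classified as elevated whatever their reading.

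Three stronger inferences are not supported:
- **That the primary conclusion is at risk.** The variable enters neither the unadjusted test against 12% nor the sample size. The effect is confined to the baseline comparison and the supportive adjusted analyses.
- **That a definite fraction of syndrome cases is lost.** Under similar assumed blood-pressure distributions, 16% to 24% of cases are missed if the other four criteria are independent, but about 10% to 15% if they are correlated. The documents supply none of these inputs.
- **That the MACE comorbidity factor is seriously affected.** SAP 2.8.1.1 sets that factor by the presence of at least one listed condition, and it lists hypertension, glucose and waist separately from metabolic syndrome. A patient whose status changes has exactly two of waist, triglycerides, HDL and glucose, and is usually flagged already through glucose or waist. The main exceptions are triglycerides with HDL alone, and men whose waist meets the 102 cm syndrome limit but not the 120 cm limit printed in that table, without raised glucose.

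**What to change.** In SAP 2.3.2 and protocol 6.5.1, change the analysis derivation so that the component is met by systolic ≥ 130 mmHg and/or diastolic ≥ 85 mmHg, or by current antihypertensive treatment. This reconciles both sections with Appendix 1 and SAP Table 2.8.4.3, since every Appendix 1 hypertensive reading then meets the component. State explicitly that one pressure is sufficient, record the change in SAP section 4, and derive the variable this way before the baseline comparison or any model uses it.

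The cost is one word in each document and one line of code. Protocol 6.5.2 already has blood pressure measured at visits 2 and 3, so nothing new is collected, and the sample size does not change.

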The choice of the MMRM model instead of a simple ANCOVA model on changes vs week 0 considering the prevalence approach or Last observation carried forward (LOCF) approach was done because the LOCF approach would underestimate the within-group mean changes between treatments compared with MMRM, whereas the prevalence approach tend to overestimate the within-group changes (Prakash et al. 2008).

In addition to that, similar MMRM model will be fitted on LOCF and prevalence set without the propensity score approach. An unstructured covariance matrix for the repeated measures within each patient will be applied in the analysis, if the model does not converge, compound symmetry will be used. The explanatory variables in the longitudinal model include cohort, visit, cohort-by-visit interaction, age, geographical region (i.e. north vs south vs central), BMI categories (<25 vs >=25), waist circumference, smoking status, metabolic syndrome (yes vs no), age at diagnosis of psoriasis, and along with interaction terms of each factor with visit.

The SAS codes are described in appendix section.

MMRM with MI approach

MMRM analysis will be also performed using multiple imputation (MI) approach on ITT population.

The multiple imputation will be done with pattern-mixture models (PMMs) as above, that allows formulating assumptions regarding missing data in a transparent and clinically interpretable manner.

The SAS codes are described in appendix section.

PASI 75

A logistic regression analysis model will be also fitted, considering age, geographical region, BMI, smoking status, metabolic syndrome, TNF α -308 polymorphism (if feasible), as well as all clinical relevant variable resulting statistically different at baseline between cohort, as strata factors. The analyses will be done similar to primary analyses based on prevalence, LOCF and NRI approaches using ITT set.

Time to reach PASI 90

The differences between cohorts Cw6-negative and Cw6-positive in time to reach PASI 90 will be evaluated by means of a log-rank test. The hazard ratios and their corresponding 95% confidence intervals will be also computed using a stratified Cox proportional hazards regression model with Cw6 group and baseline PASI as explanatory variable and stratified by geographical region and BMI categories, as well as age categories (tertiles).

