2.14 Interim analysis

No interim analysis is planned for this study.

3 Sample size calculation

The primary objective of this study is to evaluate the clinical response in PASI 90 at week 16 of Cw6-negative and Cw6-positive psoriatic patients. According to literature data, Cw6-positive patients will be about 60% of the entire psoriatic patient population.

From a previous study with ustekinumab (Talamonti et al. 2013) we can observe a difference in response to PASI 90 between Cw6-positive vs Cw6-negative patients of around 30%, in favor of Cw6-POS. Therefore, it is sensible to expect a response in the Cw6-negative cohort not less than 12 % respect to the Cw6-positive group. Further considerations are stated in the paragraph below.

Phase III data on secukinumab show a PASI 90 response at 16 weeks of 71%. Under the assumption that 60% of all the enrolled patient population is represented by Cw6-POS patients, we can reasonably assume to observe a proportion of patients with PASI 90 of 80% in the Cw6-POS cohort.

Under these assumptions, considering a one-side alpha level of 0.025 and a power of 80%, 365 patients (219 Cw6-POS and 146 Cw6-NEG) are sufficient to evaluate if the response in terms of PASI 90 in the Cw6-negative cohort is not less than 12% respect to the Cw6-positive cohort.

Considering a dropout rate at 16 weeks of 10% equally divided in the two studied cohorts, a total of 406 patients should be enrolled.

All calculations were done with NQuery 7.0.

A power analysis based on a different Cw6 patient distribution was made in order to facilitate patient enrollment without power-loss in the primary endpoint evaluation. Table 3-1 shows how the enrollment rate should be set free until the ratio between Cw6-POS and Cw6-NEG reaches the 1:1 rate-distribution, with a power of at least 80%.

In particular, the number of Cw6-POS evaluable patients will range from 219 to 182, whereas those in the Cw6-NEG cohort will range from 146 to 182.

Based on the table below, the enrollment in one of the two cohorts will be stopped when the target number is achieved (a maximum of 244 Cw6-POS patients will be allowed).

Table 3-1:Power analysis

Power	Ratio	Cw6	Cw6	Cw6	Cw6	Overall	Cw6	Cw6	

For business use only

		POS	POS	POS	POS		POS	POS
		%	%	Ν	Ν	Ν	%	%
80%	0.66	60%	40%	219	146	365	244	163
80%	0.70	59%	41%	215	150	365	239	167
80%	0.72	58%	42%	212	153	365	236	170
80%	0.75	57%	43%	209	156	365	233	174
81%	0.79	56%	44%	204	161	365	227	179

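### Three baseline cohort comparisons in SAP 2.3.2 are adjusted for a variable that is part of what they test: metabolic syndrome for waist, and age at and time since psoriasis diagnosis for age

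*SAP*

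**What the plan says.** SAP 2.3.2 states that "the homogeneity of patient distribution between cohorts will be tested on selected baseline demographics and anamnestic variables", and metabolic syndrome is among the examples it gives. A later sentence in the same section adds further cohort differences to be explored, including age at psoriasis diagnosis and time since diagnosis. Continuous variables go into an ANCOVA and most categorical ones into a logistic model, each with the covariates in a table. The row that contains "Time since PsO diagnosis/ age at PsO diagnosis/ presence of PsA/ time since PsA diagnosis/ metabolic syndrome" has the covariates age, sex and waist.

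Two definitions in the same section matter:

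- Metabolic syndrome needs at least three of five criteria, one of which is "Increased waist circumference (≥ 102 cm for men, ≥ 88 cm for women").
- Time since diagnosis is the baseline visit date minus the date of first diagnosis.

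If data are non-normal, a non-parametric test is to be used where feasible. The test is not named, and the SAP does not say whether the covariates are kept. Crude summaries by cohort are planned for every variable.

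The results are used again in SAP 2.7.2. The PASI 75 logistic model has a fixed list that includes age and metabolic syndrome, "as well as all clinical relevant variable resulting statistically different at baseline between cohort, as strata factors".

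**The concern.** The cohorts are defined by genotype and are not randomised, so the baseline comparison is what tells a reader how alike they are. That is a question about each variable as it stands in the two cohorts. Conditioning on part of the variable changes the question.

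- **Metabolic syndrome given waist.** The test asks whether patients with the same waist differ in metabolic syndrome. A difference that arises because one cohort has larger waists is adjusted away.
- **Age at diagnosis and duration given age.** Once age is fixed, either quantity determines the other, so the two tests cannot give separate answers. If one cohort has earlier onset and is therefore younger, with the same disease duration, the age-adjusted duration test compares patients of equal age and finds longer duration in that cohort.

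At stake are the baseline p-values, and the PASI 75 covariate list so far as it depends on them.

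**Working it through.** **1. The plan's own figure.** The SAP gives no figure for the baseline tests, so the sample size was reproduced first to fix the cohort sizes. SAP section 3 says that "considering a one-side alpha level of 0.025 and a power of 80%, 365 patients (219 Cw6-POS and 146 Cw6-NEG) are sufficient". The inputs are a Cw6-positive PASI 90 rate of 80%, a 12-point margin, and a Cw6-negative rate of 80% (not stated; assumed). With ratio r = 146/219 = 0.667:

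n(POS) = (1.960 + 0.842)² × [0.16 + 0.16/0.667] / 0.12² = 7.849 × 0.40 / 0.0144 = 218.03, rounded up to 219.

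n(NEG) = 218.03 × 0.667 = 145.4, rounded up to 146. The total is 365, and 365/0.9 = 405.6 gives 406. The plan's figures are reproduced. All checks below use 219 and 146, two-sided 0.05 (the SAP states no level for baseline tests) and 2,000 simulated trials per scenario.

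**2. Metabolic syndrome.** Assumed: waist SD 13 cm; the other four criteria correlated 0.3 or 0.5 with waist on a latent scale; the cohort difference acts only through waist.

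| Correlation | Waist shift (SD) | Prevalence | Unadjusted | Age, sex | Age, sex, waist (SAP) |
|---|---|---|---|---|---|
| 0.3 | 0.3 | 39% v 32% | 28.2% | 29.4% | 5.1% |
| 0.3 | 0.4 | 42% v 32% | 43.8% | 45.7% | 4.6% |
| 0.3 | 0.5 | 44% v 33% | 61.6% | 65.5% | 4.8% |
| 0.5 | 0.3 | 44% v 35% | 40.1% | 42.0% | 4.6% |
| 0.5 | 0.4 | 47% v 35% | 61.9% | 64.6% | 4.0% |
| 0.5 | 0.5 | 50% v 35% | 80.8% | 83.8% | 4.6% |

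The last three columns are rejection rates. If the shift (0.3-0.4) lies in the other four criteria and waist is equal, the order reverses: 88-99% with waist in the model against 61-92% unadjusted.

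**3. Age at diagnosis (O) and duration (D) given age (A).** Since O = A − D, and A is in the model, regressing O on cohort, A, sex and waist gives a cohort coefficient equal to minus that from regressing D on the same terms. The residuals change sign only, so the standard error and p-value are the same. This holds for any data, up to rounding of age. In simulation the largest discrepancy was about 5e-12.

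**4. Size of the duration artefact.** Assume that O and D are independent within cohort, with SDs sO and sD. The slope of D on A is β = sD²/(sD² + sO²). If the cohorts differ by dO in onset and dD in duration, the age-adjusted duration difference is dD − β(dO + dD).

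For sO = 14, sD = 12, dO = −5, dD = 0: β = 144/340 = 0.424, and the difference is 0.424 × 5 = 2.12 years, although the true value is 0. The simulation gave 2.13. Rejection rates of the SAP ANCOVA with equal duration, and mean adjusted difference in years:

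| sO / sD (years) | Onset 3 y earlier | 5 y earlier | 8 y earlier |
|---|---|---|---|
| 15 / 10 | 18.3% (0.95) | 40.3% (1.54) | 76.8% (2.45) |
| 14 / 12 | 25.4% (1.27) | 58.5% (2.13) | 93.2% (3.39) |
| 12 / 12 | 35.3% (1.46) | 78.4% (2.51) | 98.6% (3.97) |

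In the same scenarios the unadjusted t-type test rejects in about 4-7% and the unadjusted rank test in about 5-7%.

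Two further cases follow from the formula. With equal ages (dO = −5, dD = 5) the adjusted difference is 5 years, which is correct. With equal onset and a true 4-year duration difference it shrinks to 4(1 − β) = 2.0-2.8 years, and rejection falls from 88-97% to 59-87%. With no difference in either, the test keeps its level (4-5%).

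**The case against.** The strongest reply is that the imbalance would usually be seen elsewhere in the same output. Waist is tested separately, with age and sex only. Ignoring those covariates, its power is about Φ(shift × √(219 × 146/365) − 1.96) = Φ(9.36 × shift − 1.96), which is 80%, 96% and 99.7% for shifts of 0.3, 0.4 and 0.5 SD. Age is also tested, adjusted for sex only. Crude counts, percentages and means by cohort are reported for all these variables. This stands: a p-value may mislead, but the data are not concealed.

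The second reply is the non-parametric fallback. Disease duration is likely to be skewed. With a gamma-shaped duration (mean 17.6, SD 12 years), Shapiro-Wilk rejected normality of the raw values in every run and of the ANCOVA residuals in 93-94%. An unadjusted rank test then rejected in 6.0%, 5.4% and 4.5% for onset shifts of 3, 5 and 8 years. This stands in part. The fallback applies only if feasible, its covariates are unspecified, and it cannot help metabolic syndrome, which is binary.

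Third, comparing disease history at a given age is a legitimate question, and the SAP writes down no formal null hypothesis. That is fair. It still leaves two planned ANCOVAs that can only return one result.

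A reader might infer that the SAP will hide a metabolic syndrome imbalance or will produce a false duration imbalance. The documents do not support either as a certainty. The first needs the imbalance to run through waist; the second needs an onset difference that carries into current age. The documents report neither.

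A reader might also infer that efficacy results are compromised. The primary test is an unadjusted difference in proportions. Its logistic model (SAP 2.5.2) fixes age, waist, metabolic syndrome and age at diagnosis in advance. Metabolic syndrome is also already fixed in the PASI 75 model, so its baseline p-value selects nothing there.

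**Conclusion.** The point holds as a defect in three comparisons. Two parts need no assumption: the metabolic syndrome test conditions on one of its own criteria, and the two age-adjusted ANCOVAs on diagnosis timing are one test reported twice. The rejection rates do rest on assumed shifts, SDs, correlations and a 0.05 level, none of which the documents give. They show what can happen, not what is expected.

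The reach into efficacy is narrow. Under the ANCOVA, age at diagnosis and duration either both qualify for the PASI 75 model or neither does. If both enter, they join age, already in the model, and the three are exactly or nearly collinear. With age entered linearly, adding either one gives the same fit, so the harm is a badly formed rule more than a biased cohort estimate. The change is worth making because these p-values are meant to support interpretation of non-randomised cohorts and the edit is small.

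**What to change.** In the SAP 2.3.2 table:

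- Take metabolic syndrome out of the shared row and test it without waist.
- Take age at psoriasis diagnosis and time since psoriasis diagnosis out of that row and test them without age.
- For these three variables, report the crude cohort difference with its 95% CI.

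In the PASI 75 paragraph of SAP 2.7.2, replace selection by baseline significance with a fixed covariate list, as SAP 2.5.2 does for the primary model. Use at most one of age at diagnosis and duration alongside age.

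The other rows need not change. The evidence here does not extend to removing covariates from every comparison or to making standardised differences the balance criterion; those would be matters of preference.

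The cost is a few table cells, one sentence and slightly simpler code. The downside is that crude imbalances may look larger in the baseline table.
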